## 2.0 Objectives

Aim 1: Identify ancestry-informative variants in tobacco metabolism and detoxification pathway genes that correlate with metabolic/detoxification capacity in AA smokers.

Aim 2: Identify ancestry-informative variants in tobacco addiction pathway genes that correlate with measures of nicotine dependence in AA smokers.

Aim 3: Explore the possibility that genetic feedback about increased lung cancer risk associated with African American ancestry may influence perceived risk, cancer worry, acute psychological distress, and motivation to quit.

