## 3.0 Background/Rationale

*Genetics, race, tobacco-related carcinogen metabolism, and addiction.* Two prominent groups of potent tobacco carcinogens are benzo[a]pyrene and tobacco-specific nitrosamines such as N'-nitrosonornicotine (NNN) and 4-(methylnitrosamino)-1-(3-pyridyl)-1-butanone (NNK). NNK is reduced in the body to NNAL and activated by Phase I enzymes to a reactive metabolite that alkylates DNA or is further detoxified by Phase II enzymes in the *UGT* pathway to NNAL – glucuronide (NNAL-Gluc). Phase III enzymes (ABC transporters) are known to efflux Phase II conjugates from cells to enable excretion from the body. NNAL is a potent carcinogen in rats. Studies demonstrate that urinary NNAL-Gluc:NNAL ratio, a measure of an individual's metabolism and detoxification capacity, is higher in Whites compared to AA, suggesting racial differences in metabolic activation/detoxification of tobacco smoke carcinogens. Genetic polymorphisms have been described for a number of Phase I, II/III enzymes involved in the metabolism of tobacco and efflux of carcinogens. Many of these polymorphisms have been linked to phenotypic differences in protein activity or expression and are likely to be a major source of inter-individual variation in susceptibility to tobacco carcinogenesis and thus increased lung cancer risk. Levels of urinary NNAL metabolites can be influenced by polymorphisms in the Phase I and II genes, highlighting the importance of genetic variants in tobacco metabolism and carcinogenesis.

Interestingly, the association of genetic variants in Phase I/II/III genes with the metabolism and efflux of tobacco smoke carcinogens from cells may prove to be dependent on race, because the frequency of these polymorphisms varies among racial/ethnic groups. Our preliminary data presented below also provides further support by demonstrating that in Phase I/II/III genes,

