#### *4.1 Subject Recruitment and Data Collection*

**Face-to-face:** As previously described in IRB 11-880, study subjects will be recruited from various locations throughout the metropolitan area of the aforementioned study cities (for example, stores, shops, community centers, senior centers, health fairs etc.). Based on results from protocol 11-880, we have determined that "on-site" (face-to-face) recruitment from various locations throughout the Philadelphia metropolitan area works best for control recruitment; subsequently, we will use this method as the primary recruitment method for this study. Primary care and specialty clinics within TUHS (e.g. ENT and Pulmonary clinics) to identify current smokers. We will also utilize study flyers (attached in recruitment section) throughout the TUHS with the contact information for study staff. If the individual calls in we will answer any questions and schedule their enrollment during their next appointment at a TUHS clinic.

After informed consent is obtained Mouthwash/Saliva samples will be collected at the completion of the study questionnaire. Participants will be supplied with a 50 mL falcon tube containing 10ml of scope. Participants will be instructed to gargle while tilting to the back of the throat for 30-60 seconds before spitting it back into a separate tube. Participants will be required to have refrained from eating and drinking at least 30 minutes prior to performing the mouthwash rinses. All mouthwash samples will be transported at 4 degrees Celsius (on ice packs) to the laboratory where they will be processed. All samples will be labeled with a unique ID number corresponding to the questionnaire but without personal identifiers. For urine collection, study staff will instruct the participant on how to conduct a clean catch urine sample and the participant will self-collect in nearest rest room.

All participants with a history of cancer screening (e.g. Pap test, breast mammography [females], PSA and/or DRE [males], oral or skin cancer screening, etc.) within the past 12 months will be asked to sign an authorization to request information from another facility. We will use the standard authorization form used by Fox Chase

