### 13.0 Statistical Analysis

**Aim 1:** Variance stabilizing and normalizing transformations will be applied when appropriate. Descriptive statistics for demographic variables will be presented. The range and mean concentrations of free (NNAL), conjugated (NNAL-Gluc) and total (NNAL+NNAL-Gluc) biomarkers will be summarized by genotype. These concentrations as well as the ratio of NNAL-Gluc:NNAL concentrations will be correlated with each AIM after adjusting for smoking dose (pack-years), age and recruitment setting (clinic vs. community) using analysis of variance. A similar analysis will be done by correlating these variables with each haplotype block. In addition, multiple linear regression will be used to correlate NNAL concentration with proportion of African ancestry after adjusting for smoking dose, age and recruitment setting. To account for multiple testing, the Benjamini-Hochberg (BH) method will be used to control the false discovery rate (FDR). All tests will be two-sided and tests with  $FDR \leq 10\%$  will be considered to be statistically significant.

**Sample Size and Power:** With 360 samples split in a 1:3 ratio between the minor and major allele groups, we will have 80% power to detect an effect size of 0.45 in mean NNAL concentration (total) between the groups using a two-sided test at a significance level of 0.005. This computation is based on a standard deviation of 1 for NNAL concentrations (on the log2-scale) from pilot studies. An effect size of 0.45 corresponds to a 1.37-fold change in NNAL concentration between groups. Similarly, with 360 samples split in a 1:3 ratio between the minor and major allele groups, we will have 80% power to detect an effect size of 1.09 in mean NNAL concentration ratio between the groups using a two-sided test at a significance level of 0.005. This computation is based on a standard deviation of 2.44 for NNAL concentration ratios (on the log2-scale) from pilot studies. An effect size of 1.09 corresponds to a 2.13-fold change in NNAL expression between groups. A significance level of 0.005 results in 1 false discovery per 200 non-differentially expressed SNPs.

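### The Aim 1 regression on African ancestry uses NNAL concentration as its only outcome, so that regression cannot separate detoxification capacity from tobacco uptake or urine dilution

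*Combined protocol and SAP*

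**What the plan says.** Section 2.0 sets Aim 1 as finding variants "that correlate with metabolic/detoxification capacity in AA smokers". Section 3.0 says how that capacity is measured: "urinary NNAL-Gluc:NNAL ratio, a measure of an individual's metabolism and detoxification capacity". It adds that the ratio is higher in Whites than in African Americans, which is part of the motivation for the study.

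Section 13.0 (Aim 1) summarises free, conjugated and total NNAL. For the variant tests it says: "These concentrations as well as the ratio of NNAL-Gluc:NNAL concentrations will be correlated with each AIM". The same variables are then carried to the haplotype blocks, and the ratio has its own power statement. A further model is added: "multiple linear regression will be used to correlate NNAL concentration with proportion of African ancestry after adjusting for smoking dose, age and recruitment setting". The ratio is not named in that model, nor is NNAL specified as free or total. Smoking dose is defined as pack-years.

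On the specimen, Section 4.1 says "study staff will instruct the participant on how to conduct a clean catch urine sample", and that the participant collects it unsupervised. No creatinine, specific gravity or timed collection is mentioned anywhere. The transformations in Section 13.0 are for variance and normality, not dilution.

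**The concern.** The ancestry regression is the one Aim 1 model that relates the urinary phenotype to overall African ancestry, and it omits the quantity whose racial difference Section 3.0 reports. Concentration is not a substitute. It depends on how much NNK was taken up, on how much NNAL was glucuronidated (for free NNAL) and on how dilute the urine was.

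Pack-years is a cumulative history measure and only partly captures current intake. Section 1.0 itself notes that African American smokers smoke fewer cigarettes but inhale more deeply and for longer, so uptake could differ at equal pack-years. A positive result could therefore be read as a detoxification difference when it reflects exposure. A null result would say little about detoxification, particularly if total NNAL is used.

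**Working it through.** **1. The plan's own power figures.** Inputs from Section 13.0: 360 samples split 1:3 (90 and 270), two-sided alpha 0.005, log2 SD 1 for concentration and 2.44 for the ratio.

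- Standard error factor: sqrt(1/90 + 1/270) = 0.1217.
- Concentration: 0.45 / 0.1217 = 3.70; 3.70 − 2.807 = 0.89; power 81.3% (80.8% with the noncentral t).
- Ratio: 1.09 / (2.44 × 0.1217) = 3.67; 3.67 − 2.807 = 0.86; power 80.6% (80.0% with the noncentral t).
- Fold changes: 2^0.45 = 1.37 and 2^1.09 = 2.13.

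The stated 80% and both fold changes reproduce. These figures concern the two-group allele contrasts. The plan gives no power figure for the ancestry regression.

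**2. What each outcome contains.** Let T be true total NNAL, R the true NNAL-Gluc:NNAL ratio and d a dilution factor common to both analytes in one sample.

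- Measured free = d·T/(1+R)
- Measured conjugated = d·T·R/(1+R)
- Measured total = d·T
- Measured ratio = R

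The ratio contains neither d nor T. The total contains both and, with T held fixed, nothing of R. Free NNAL contains all three. For the plan's 2.13-fold change in R with T fixed, log2 free NNAL changes by −log2[(1 + 2.13R)/(1 + R)]. This is −0.46 at R = 0.5 and −0.93 at R = 4 (baseline ratios are assumed; the documents give none). Total NNAL changes by 0. Whether NNAL means free or total therefore matters.

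**3. Precision or bias from dilution.** The documents give no dilution SD, so the values here are assumptions. Simulation: n = 360, 4,000 runs per setting, no true ancestry effect, nominal two-sided 5%, no covariates, concentration SD 1 including dilution.

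| Correlation of dilution with ancestry | Dilution SD (log2) | False positives, concentration | False positives, ratio |
|---|---|---|---|
| 0 | 0.5 | 4.6% | 4.5% |
| 0 | 0.7 | 4.8% | 4.5% |
| 0.1 | 0.5 | 15.9% | 5.2% |
| 0.1 | 0.7 | 26.4% | 4.9% |
| 0.2 | 0.5 | 47.5% | 4.6% |
| 0.2 | 0.7 | 76.4% | 4.6% |

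If dilution is unrelated to ancestry, the test keeps its level and only precision suffers. The inflation in the lower rows requires a dilution–ancestry correlation, for which the documents give no evidence.

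**4. What the ancestry regression can detect.** With three covariates (smoking dose, age, setting), Fisher's z gives r = tanh[(z for alpha + z for power)/sqrt(360 − 3 − 3)].

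- Alpha 0.005: tanh[(2.807 + 0.842)/18.815] = tanh(0.194) = 0.19.
- Alpha 0.05: tanh[(1.960 + 0.842)/18.815] = tanh(0.149) = 0.15.

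This does not depend on the outcome's scale. On the plan's SDs, 0.19 corresponds to about 0.19 × 1 = 0.19 log2 units per SD of ancestry for concentration, and 0.1915 × 2.44 = 0.47 for the ratio.

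**The case against.** The strongest reply is that Aim 1 is about variants, and the variant question is tested with the right measure: the ratio is an outcome for each AIM and each haplotype block and is powered separately. The ancestry regression is an addition. This stands. A reader might infer that the plan leaves detoxification capacity unexamined; Section 13.0 does not support that.

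Second, a reader might infer that the concentrations are known to be uncorrected. The documents contain no account of the NNAL assay. Section 12.0 says only that laboratory work is done at the coordinating centre, so a creatinine correction cannot be ruled out. That it was a single spot sample is also an inference from the collection described. This stands too, but a correction would remove only dilution; concentration would still mix uptake with detoxification.

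Third, it is tempting to say that dilution biases the ancestry result. That holds only if dilution is related to ancestry given the covariates, which nothing in the documents shows.

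Fourth, it is tempting to claim a power gain, either from the new outcome or from a smaller multiple-testing family under a single primary outcome. The detectable partial correlation is the same for both outcomes. Section 13.0 does not give the number of AIMs or say that the four Aim 1 outcomes form one family. Naming one primary outcome for the AIM tests is a preference and is not part of this point.

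Finally, exposure is a legitimate question for a concentration outcome, and the model does adjust for pack-years. That is a reason to keep the concentration regression, not to omit the ratio.

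**Conclusion.** The point holds for the ancestry regression only. The document defines detoxification capacity by the ratio, reports the racial difference in the ratio and uses the ratio in its variant tests, but then relates African ancestry to concentration alone. Followed as written, that regression cannot tell detoxification from uptake or, absent a stated correction, from dilution.

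The consequence is for interpretation. Sensitivity is unchanged on the correlation scale: a partial correlation of about 0.19 is detectable for either outcome with 360 analysable participants, three covariates, alpha 0.005 and 80% power. No bias is shown. The cancellation of dilution assumes one factor common to both analytes in the same sample, and the statement that total NNAL carries no direct detoxification signal assumes total NNAL is held fixed. This is worth correcting before analysis, and it does not undermine Aim 1.

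**What to change.** In Section 13.0, Aim 1:

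- Make log2(NNAL-Gluc:NNAL) the main outcome of the regression on proportion of African ancestry, with the covariates already listed.
- Keep NNAL concentration as an additional outcome of that regression, described as a measure of exposure, and state whether it is free or total.
- State whether any dilution correction is applied. If urinary creatinine is already measured, add its log as a covariate in the concentration models. The main change does not depend on this.

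The cost is a wording change and one more regression on data already collected, with no new participants or assays. The concentration result becomes secondary in the ancestry analysis.

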**Aim 2:** For each SNP, nicotine dependence (as determined by high-very high FTND scores: 6-10) will be modeled using genotype after adjusting for smoking dose (pack-years), age and recruitment setting using logistic regression (LR). Sensitivity, specificity and prediction accuracy (along with 95% confidence bounds) will be used to characterize the precision of binary predictions from LR. Multiple linear regression will be used to correlate the proportion of African ancestry with FTND score (low vs. high) after adjusting for smoking dose, age and recruitment setting. All tests will be two-sided and the Benjamini-Hochberg method will be used to account for multiple testing. Secondary outcomes will include cigarettes per day, age at initiation, and intention to quit. To account for the potentially large number of SNPs resulting from this univariate analysis, penalized logistic regression (PLR) will be used to develop a prediction model for nicotine dependence using these SNPs. PLR has been demonstrated to have excellent power to identify covariate effects as well as superior prediction accuracy compared to competing methods like Classification and Regression Trees and Multifactor Dimensionality Reduction. Sensitivity, specificity and prediction accuracy (along with 95% confidence bounds) will be used to characterize the precision of binary predictions from PLR. AUC curves (along with 95% confidence bounds) will be used to characterize the predictive value of models from these methods. A participant whose predictive probability is  $> 0.5$  will be classified as having high nicotine dependence; however, alternative thresholds will also be evaluated in this

analysis. In addition, the performance of each model will be evaluated using leave-one-out cross validation. All computations will be performed using R statistical language and environment.

**Sample Size and Power:** With 180 subjects each in the low-medium (scores 0-5) and high-very high (scores 6-10) nicotine dependence groups, we will have 80% power to detect a difference in the range of 0.14-0.19 (in minor allele frequency between groups in SNPs of interest) at the 0.005 significance level. This calculation assumes a 10-40% minor allele frequency in the low nicotine dependence group.

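### Aim 2 reports prediction accuracy from per-SNP models that also contain pack-years, age and setting, with no covariate-only reference, so the figures cannot show what genotype adds

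*Combined protocol and SAP*

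**What the plan says.** All of this is in section 13.0, Aim 2.

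- **Per-SNP model.** High dependence (FTND 6-10) "will be modeled using genotype after adjusting for smoking dose (pack-years), age and recruitment setting using logistic regression (LR").
- **Performance of that model.** "Sensitivity, specificity and prediction accuracy (along with 95% confidence bounds) will be used to characterize the precision of binary predictions from LR". A predicted probability above 0.5 counts as high dependence, and other cut-offs will be examined.
- **Multi-SNP model.** "penalized logistic regression (PLR) will be used to develop a prediction model for nicotine dependence using these SNPs". The text does not say whether the covariates enter it.
- **AUC.** "AUC curves (along with 95% confidence bounds) will be used to characterize the predictive value of models from these methods". I read this as covering both the logistic (LR) and the penalized (PLR) models.
- **Validation.** "the performance of each model will be evaluated using leave-one-out cross validation".
- **Association tests.** "All tests will be two-sided and the Benjamini-Hochberg method will be used to account for multiple testing".

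Neither section 13.0 nor any other section names a covariate-only model, a change in AUC or accuracy, or any other reference value for these measures.

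**The concern.** Predictions from a per-SNP model use genotype and three covariates together. Pack-years measures smoking, so it can be expected to track dependence. Section 4.0 justifies recruiting from clinics and the community partly by the wider spread of smoking and dependence it should bring. With no stated reference, a reader will compare the accuracy with chance, which is 0.50 at the planned split of 180 and 180. An accuracy of 0.63 with a lower bound above 0.50 then looks like a predictive variant, even if the SNP contributes nothing. At stake is the meaning of the prediction results, which the plan presents alongside the association tests.

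**Working it through.** **1. The plan's own figure.** The only numerical claim for Aim 2 is 80% power at the 0.005 level for a difference of 0.14-0.19 in minor allele frequency, with 180 per group and 10-40% in the low-dependence group. Using n = [z(α/2)·√(2p̄q̄) + z(β)·√(p₀q₀ + p₁q₁)]² / d², with z values 2.807 and 0.842 and n = 180:

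- p₀ = 0.10: d = 0.145 (arcsine version 0.142)
- p₀ = 0.40: d = 0.192 (arcsine version 0.191)

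The figure reproduces within rounding and is not in dispute.

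**2. Simulation set-up.** There were 1,000 runs per scenario.

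- From the documents: N = 360, half clinic and half community; about half with high dependence; cut-off 0.5; leave-one-out (computed by the standard one-step approximation).
- Assumed: odds ratios per SD of pack-years and for setting, as tabulated; age odds ratio 1.0, with age correlated 0.4 with pack-years; minor allele frequency 0.25; SNP with no effect.
- Lower 95% bound: accuracy − 1.96·√[accuracy·(1 − accuracy)/360].

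**3. Mean leave-one-out accuracy for a SNP with no effect**

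| Assumed OR, pack-years / setting | Covariates + SNP | Covariates only | SNP only | Runs with lower bound above 0.50 |
|---|---|---|---|---|
| 1.0 / 1.0 | 0.503 | 0.502 | 0.503 | 7% |
| 1.3 / 1.3 | 0.545 | 0.547 | 0.500 | 44% |
| 1.5 / 1.5 | 0.576 | 0.578 | 0.500 | 82% |
| 2 / 2 | 0.635 | 0.637 | 0.500 | 99.9% |
| 3 / 2 | 0.690 | 0.692 | 0.504 | 100% |

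For example, at 0.635 the lower bound is 0.635 − 1.96·√(0.635 × 0.365/360) = 0.635 − 0.050 = 0.585. At odds ratios 2/2 the AUC is 0.683 with the SNP and 0.685 without it.

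**4. A SNP with a real effect** (per-allele odds ratio 1.8, covariates 2/2). Accuracy is 0.647, against 0.633 for covariates only in the same runs; AUC is 0.700 against 0.680. Compare the absolute accuracies: 0.647 for the real SNP and 0.635 for the null one. They hardly differ. The mean differences from the benchmark do separate the two:

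- accuracy: +0.015 (real) and −0.002 (null)
- AUC: +0.020 (real) and −0.002 (null)

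These differences are noisy in one study. For the real SNP their SDs across runs are 0.020 for accuracy and 0.0145 for AUC, so they need intervals.

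**5. The association test in the same runs.** The adjusted SNP test gave p < 0.005 in 0.1% to 0.5% of null runs and in 62.5% of runs with the real SNP. It works as intended.

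**6. Cross-check by another route.** Let pack-years and latent dependence be bivariate normal with correlation r, with dependence cut at the median. Then accuracy = 0.5 + arcsin(r)/π. This gives 0.564 at r = 0.2 and 0.667 at r = 0.5; the corresponding AUCs are about 0.59 and 0.73. These values of r are also assumptions.

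**The case against.** **The SNP's contribution is already tested.** The adjusted genotype test asks whether the SNP adds to the covariates, with false-discovery control, and section 2.0 frames Aim 2 as a question of correlation. This stands. A reader might infer that null SNPs would be declared associated or carried forward because their models look accurate. The documents do not support that: no SNP is selected on accuracy. For the same reason, a further likelihood-ratio test per SNP would add little. But a p-value does not say how much of a reported accuracy is genetic.

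**The plan describes models, not SNPs.** Its wording credits predictions and models, so it does not itself attribute the accuracy to genotype. A table of many SNP models with near-identical accuracy would also hint at the baseline. Both points are fair, but a stated benchmark is better than one the reader must guess.

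**Leave-one-out cross-validation.** It corrects for overfitting, not for the covariates' share. The accuracies in the table are already leave-one-out.

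**The covariate effects are assumed.** True. Section 4.0 credits the wider range of dependence to the recruitment strategy as a whole and gives no association between setting and dependence.

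**Two further readings to avoid.** One is that PLR uses SNPs alone and so cannot be compared with LR. The text says neither that covariates are in nor that they are out; if they are out, they cannot inflate PLR accuracy. The other is that one SNP at the detectable difference discriminates far less than smoking dose. Treating allele frequency as one binary marker per person gives AUC 0.5 + d/2, or 0.57-0.60. The plan models genotype, and allele counts under Hardy-Weinberg give 0.62-0.64. That lies inside the assumed 0.59-0.73 for smoking dose, so no such gap is shown.

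**Conclusion.** The point holds for the prediction measures of the per-SNP logistic models. Reported without a covariate-only reference, their sensitivity, specificity, accuracy and AUC cannot show what genotype adds. The size depends on covariate effects that the documents do not give: none at odds ratios of 1.0, and an accuracy of 0.545 to 0.690 for a null SNP at assumed odds ratios of 1.3 to 3. This is a gap in how prediction is reported. It does not weaken the association tests or the power statement. For PLR, the only finding is that the plan leaves the role of the covariates unstated.

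**What to change.** - Fit the logistic model with pack-years, age and setting only, on the same participants and under the same leave-one-out cross-validation.
- For each SNP model, report the difference from it in AUC, sensitivity, specificity and accuracy, with 95% confidence intervals that respect the pairing (both models score the same people). Use the same cut-off for both.
- State whether the covariates enter PLR. If they do, report the same differences. If they do not, do not compare PLR accuracy directly with that of the covariate-adjusted LR.

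The cost is one extra model and a few added table columns. No new data or participants are needed, and no test or sample size changes.

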
## 4.0 Study Design

This is a multi-centered study being conducted at the following centers:

Fox Chase Cancer Center (FCCC) by the lead investigator, [name], MPH. FCCC will serve as the coordinating center for this study.

CUNY Hunter College under the direction of [name], MPH will conduct community based research initiatives and recruit study participants from the community.

Icahn School of Medicine at Mount Sinai with [name] will obtain IRB approval, recruit subjects and execute the protocol at Mount Sinai.

We will enroll 360 AA smokers, 180 from clinic-based settings in Philadelphia and NYC that serve smokers and 180 from the general community in Philadelphia and NYC. This recruitment strategy will provide a regionally-diverse sample with an increased range of smoking and dependence levels, which will enhance generalizability, as well as power to detect hypothesized genetic effects. To ensure that the demographics of both clinic and community-based samples are balanced, both subgroups will be matched on age and gender.

Subjects that had participated in protocol 14-814, PI [name]'s cohort of cancer-free individuals and indicated they would like to be contacted for possible participation in future research will be offered an opportunity to enroll in this study. These participants will complete the intervention aspect of the study and we anticipate they will help us to reach our recruitment goals. This protocol enrolled subjects in NYC and Philadelphia. It also allowed those enrolled to be notified of other cancer related studies led by [name] and/or her collaborators.

Recruitment and study setting: Philadelphia and NYC are racially diverse, with AAs comprising a large portion of the general populations. This proposed study will leverage on our existing cohort (CAP3) infrastructure, as well as the considerable resources of the Mount Sinai Health System, with which we have partnered to enhance recruitment.

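### Aim 2 cuts the 0-10 FTND score into low and high and does not name the response in the ancestry regression, which loses information and leaves the estimand unclear

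*Combined protocol and SAP*

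**What the plan says.** Section 2.0 states Aim 2 as: "Identify ancestry-informative variants in tobacco addiction pathway genes that correlate with measures of nicotine dependence in AA smokers". Section 13.0 (Aim 2) then plans two analyses of FTND.

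- **SNPs.** "nicotine dependence (as determined by high-very high FTND scores: 6-10) will be modeled using genotype". The outcome is binary and the model is logistic, with three covariates: pack-years, age and clinic or community setting.
- **Ancestry.** "Multiple linear regression will be used to correlate the proportion of African ancestry with FTND score (low vs. high"), with the same three adjustment variables. The response is not named.

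The Aim 2 power statement rests on the same cut: "With 180 subjects each in the low-medium (scores 0-5) and high-very high (scores 6-10) nicotine dependence groups, we will have 80% power". The detectable effect printed there is 0.14-0.19, as a difference in minor allele frequency tested at the 0.005 level, when that frequency is 10-40% among those with low dependence. No power figure is given for the ancestry regression.

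Aim 2 plans no analysis of the whole score and gives no reason for the cut. The only FTND distribution implied is the assumed 180/180 split. Cigarettes per day, age at initiation and intention to quit are secondary outcomes.

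**The concern.** From the ancestry sentence an analyst could fit three different models:

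- a linear model for the low/high indicator, giving a risk difference;
- a linear model for ancestry proportion with FTND group as predictor, giving a difference in ancestry;
- a linear model for the score itself, giving FTND points.

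These are different estimands, and the choice would be made after the data are in.

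The cut also treats scores 5 and 6 as opposites and scores 6 and 10 as the same. Section 4.0 defends the recruitment strategy partly because it widens the range of dependence levels and so helps power for genetic effects. Collapsing the score to two groups gives away the range within each group. Section 4.0 fixes numbers by recruitment setting and matches on age and gender, but nothing controls the FTND split on which the power of a binary analysis depends.

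**Working it through.** **1. The plan's own figure.** Inputs from section 13.0 (Aim 2): 180 per group, two-sided alpha 0.005, 80% power, low-group frequency p1 of 0.10 to 0.40. With p2 = p1 + d and m = (p1 + p2)/2, the pooled normal approximation is

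power = Φ{[d√n − z√(2m(1−m))] / √(p1(1−p1) + p2(1−p2))}, z = 2.807.

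Solving for d at 80% power:

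| p1 | d |
|---|---|
| 0.10 | 0.1446 |
| 0.20 | 0.173 |
| 0.30 | 0.187 |
| 0.40 | 0.1915 |

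These round to the printed 0.14-0.19, so the figure reproduces.

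**2. Does linear versus logistic matter?** Simulation with n = 360, 1,500 runs, alpha 0.05. Assumed: ancestry proportion with mean 0.8; adjustment for pack-years, age and setting; a normal latent trait (centre 5.5, residual SD 2.3) rounded and limited to 0-10; high = 6 or more.

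| Model | Rejection, no effect | Power, one assumed effect |
|---|---|---|
| Linear, 0-10 score | 5.5% | 80.1% |
| Linear, low/high | 4.4% | 60.7% |
| Logistic, low/high | 4.2% | 60.6% |
| Linear, ancestry as response | 4.4% | 60.7% |

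The simulation standard error is about 0.6 points in the first column, √(0.05 × 0.95/1500), and at most about 1.3 in the second. The three cut-score models are indistinguishable. The power loss comes from the cut.

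**3. Size of the loss.** For a normal trait with upper fraction p above cut point c, the efficiency of the split relative to the trait is φ(c)²/[p(1−p)].

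- p = 0.5: 0.3989²/0.25 = 0.637, a loss of 36%; 360 people carry the information of about 229.
- p = 0.4, 0.3, 0.2: losses of 38%, 42% and 51%.

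For a discrete 0-10 score, the efficiency is the squared correlation between the score and the indicator of 6 or more.

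- Rounded normal, SD 2 to 3, split 50/50: loss 31-34%.
- Rounded normal with 16-43% high: loss 32-53%.
- Flat 0-10: variance 10, p = 5/11, covariance 15/11, so (225/121)/(10 × 30/121) = 0.75, a loss of 25%.
- U-shaped or two-peaked: efficiency about 0.85, a loss of about 15%.

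**4. What this means for power.** Take a test on the score that has 80% power. Its noncentrality is 2.807 + 0.842 = 3.649 at alpha 0.005, or 1.960 + 0.842 = 2.802 at alpha 0.05. Multiply by the square root of the efficiency, subtract the critical value, and read off Φ.

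| Efficiency | alpha 0.005 | alpha 0.05 |
|---|---|---|
| 0.637 (normal, 50/50) | 3.649 × 0.798 − 2.807 = 0.105, 54% | 2.802 × 0.798 − 1.960 = 0.276, 61% |
| 0.75 (flat) | 3.649 × 0.866 − 2.807 = 0.353, 64% | 2.802 × 0.866 − 1.960 = 0.467, 68% |
| 0.85 (two-peaked) | 3.649 × 0.922 − 2.807 = 0.557, 71% | 2.802 × 0.922 − 1.960 = 0.623, 73% |

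**The case against.** The plan's verb is correlate. The parallel Aim 1 sentence names the biomarker first and ancestry second, with the biomarker as the natural response. Read the same way, the Aim 2 sentence makes ancestry proportion the response, and a linear model suits a continuous response. An adjusted association can be tested in either direction. This stands: a reader might infer that the plan fits the wrong model to a binary outcome, but that is only one reading, and step 2 shows that even then the test behaves as logistic regression does. What remains is the unnamed response and the reporting scale.

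A reader might also take a loss of a third or more as a minimum. The documents do not support that. It assumes a roughly normal score, and flat or two-peaked scores lose less.

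Finally, the binary outcome is used consistently for the SNPs. The logistic models, the sensitivity and specificity, the penalized classifier and the power figure all rest on the cut at 6, and that figure already allows for it. Making the score the main SNP test would leave the only Aim 2 power statement describing another analysis. A replacement would need an FTND standard deviation that the documents do not give, and SNPs would be screened on one outcome and classified on another. This also stands, and it is why the score analysis of the SNPs should be an addition.

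**Conclusion.** The point holds as a matter of efficiency and clarity. The ancestry regression does not name its response, and it uses a cut version of a score that has to be known anyway. No reason is given, and section 4.0 argues for a wide range of dependence.

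The loss is about 31-36% for a near-normal score split evenly, about 25% if flat and about 15% if two-peaked. For a near-normal score split unevenly it reaches about 50% when only about a fifth are high. Every shape examined shows some loss. All of these rest on assumed FTND distributions, and the comparison of linear with logistic regression rests on one simulated setting.

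Two stronger conclusions do not follow. The planned tests are not invalid, and the 0.14-0.19 detectable difference is not wrong: it describes the dichotomised comparison and reproduces.

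**What to change.** - **Ancestry regression.** Name the 0-10 FTND score as the response and African ancestry proportion as the predictor, keep the adjustment for smoking dose, age and recruitment setting, and use robust standard errors. If low/high is also reported, use logistic regression for it.
- **SNPs.** Add a prespecified analysis of the 0-10 score (linear or ordinal, additive genotype) beside the planned logistic model, and say in advance how it enters the Benjamini-Hochberg adjustment. Keep FTND of 6 or more for the stated power, the penalized classifier and clinical reporting.

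This needs changes to the analysis text and a small amount of extra analysis, with no new data. The ancestry effect would be reported in FTND points, with any odds ratio given alongside.
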